10.1 Regulatory, Ethical, and Study Oversight Considerations

10.1.1 Informed Consent Process

Upon receiving the invitation email, the potential participant will select to follow the study link. In the study web page, the user will be provided with information related to the study and consent to participate in the study. They will be informed that if they choose to respond to the questions and submit their responses, they are providing consent. They will agree to participate in the research by selecting "Yes" to "Do you agree to participate in this study?". No signature will be collected as the intent is for the study to be completely anonymous.

Waiver of signed consent was selected for this study in order to be able to ensure the anonymity of the participant in this cross-sectional post-elective-intervention study. Since participants previously elected to use the Mosie Kit and now are selecting to share their experiences and perceptions about it, they need only share these experiences; there is no reason to collect any identifying information for this one time survey.

10.1.1.1 Consent/assent and Other Informational Documents Provided to participants

A consent form describing in detail the study procedure and risks will be displayed to the participant upon access to the study website using the link provided in the email. Each participant will be able to read and provide consent. The participant may print the displayed consent. Additionally, the email will contain a link to a Frequently Asked Question Document where the participant can learn more about the study.

10.1.1.2 Consent Procedures and Documentation

After reading the consent form, the participant can elect to proceed to the survey or conclude the survey. The only documentation collected about the consent is whether or not the participant elected to respond to the questions. A consent is not required for participation in this study. Answering the questions and submitting the responses provides consent. Only completed surveys that are submitted will end up in the database.

10.1.2 Study Discontinuation and Closure

It is not expected that the study will end prematurely. The expected total duration of study data collection is approximately 30 days. However, if the minimum number of surveys are not collected within the 30 day time-frame, the study will continue collecting data for up to 90 days. Since this is a one-time anonymous survey there is no reason to follow up with the participant. There is also no way to follow up with any given participant should there be a desire to do so since the surveys will be responded to completely anonymously.

Should there be any reason to discontinue the study prematurely, the PI will advise the study Sponsor and the institutional review board (IRB) of this occurrence. Circumstances that might warrant termination or suspension might include:

- Difficulties with the data capture/survey technology
- Difficulties with participant recruitment
- Data that are not sufficiently complete and/or evaluable
- Determination of a need to prematurely complete the study as determined by the PI,
 Sponsor, IRB or regulatory agency.

The study may resume once concerns about data quality and data security are addressed, and satisfying any requirements of the Sponsor, IRB, or regulatory agency.

The study may be terminated prematurely if sufficient surveys are completed prior to the 30 days of data collection. This will be done at the discretion of the Primary Investigator (PI).

10.1.3 Confidentiality and Privacy

Participation in this study is completely anonymous. Participants will receive an invitation email with a generic link to the study website. Once informed about the study and its participation, the participant can respond to the survey questions without entering any identifiable information. The PI deemed the value of obtaining any identifying information was inferior to protecting the participant's privacy and that it was unnecessary for this study. Therefore, no identifying information will be collected. There will be no identifiers that can link directly back to an individual. While information about race, gender, and age will be collected, it will not be possible to point the information back to any given individual.

Invitations to participate will be sent out by the Sponsor company. The full list of those emails will never be released to the PI. This will help keep the information from being able to be linked back to the group of emails sent.

The final database will be an anonymous database that will be the property of the Sponsor. There is currently no intent to share the results of that study beyond this research. There is an intent to publish the findings of the study as a journal article and for information on the Sponsor's company website, but this information will be limited to aggregate results and to discussions related to the findings. The Sponsor might also use aggregate data or results in future marketing materials.

10.1.4 Future Use of Stored Specimens and Data

Specimens are not part of this study. Therefore no storage of specimens is required.

Data collected for this study will be analyzed and stored as an anonymous de-identified database in the possession of the PI and at Mose Baby. The archived data will be stored for use by Mosie Baby. No one will be given access to the raw study data without the written consent of the PI or Mosie Baby.

10.1.6 Safety Oversight

Safety oversight is provided by the Institutional Review Board (IRB) who is responsible for independently reviewing this study to ensure protection of human subjects. This study will seek exempt approval Category2(i) since the research is an observation of public behavior and the information obtained is recorded in such a manner that the identity of the human subjects cannot be readily ascertained, directly or through identifiers linked to the subject.

10.1.7 Clinical Monitoring

N/A

10.1.8 Quality Assurance and Quality Control

This one time survey does not require clinical monitoring or an external QA process. Quality Assurance is conducted to ensure the quality of data is complete and that appropriate documentation is in place to support and conduct the study.

Quality Control (QC) Procedures will be implemented as follows:

- Informed Consent PI and Sponsor will both review the documentation of the
 consenting process. This review will be conducted in compliance with GCP, accuracy
 and completeness. Feedback will be provided to the PI and Sponsor in order to ensure
 proper consenting procedures are followed. The Institutional Review Board will also
 review and provide feedback on this process.
- Source Documents and the electronic data The electronic data capture will constitute the source documents for this study. The data will be entered by the participant directly into the final study database.
- Intervention fidelity This is a retrospective observational study of people using the
 Mosie Kit. Part of data collection will include information about the use of the kit and how
 it was used. This information will be used to determine whether the person used the kit
 as intended thus confirming the intervention fidelity occurred voluntarily prior to
 participation in the study.
- Protocol Deviations There is no directed intervention for this study. Therefore, protocol deviations with respect to an intervention are not expected. If any deviations occur with relation to how the data is collected or the participants recruited, that will be collected as part of the study documentation.

There is no expectation that independent monitoring would be necessary. However, if it is required, the necessary arrangements will be made.

10.1.9 Data Handling and Record Keeping

The following section pertains to data handling and record keeping. It is described in accordance with GCP standards.

10.1.9.1 Data Collection and Management Responsibilities

Google forms will be used to collect this one time survey. The only data quality checks that will be included in the survey will be those that are implemented via the appropriate selection of the type of field in order to ensure the appropriate data is entered into the field and edit checks to ensure all questions are filled in.

The online Google Form and resulting excel sheet will constitute the source data for this study. No external records or information will be combined with the survey data. Only the PI and the Sponsor will have access to download the data.

Data standards will be implemented for the study. Descriptive field names will be used for each field. All data collection is the responsibility of the PI. The PI is responsible for ensuring the accuracy and completeness of the data.

10.1.9.2 Study Records Retention

Study documents will be retained for a minimum of 3 years. No records will be destroyed without the written consent of the Sponsor. It is the responsibility of the Sponsor to inform the PI when these documents are no longer needed.

10.1.10 PROTOCOL DEVIATIONS

This protocol defines a protocol deviation as any noncompliance with the clinical trial protocol and International Council on Harmonization Good Clinical Practices (ICH GCP). The non compliance may be either on the part of the participant or the investigator. Since this is a one-time survey, no deviations are expected. If any deviations do occur, they will be documented and corrective action plans will be implemented promptly.

10.1.11 Publication and Data Sharing Policy

This study will result in data that is proprietary to the Sponsor. As such, this data will be held privately and will only be shared at the discretion of the Sponsor.

The trial will be registered with and the results of the analysis will be submitted to ClinicalTrials.gov. In addition, every attempt will be made to publish results in a peer-reviewed journal(s). Aggregate data may also be shared in any format by the Sponsor.

10.1.12 Conflict of Interest Policy

The independence of this study from any actual or perceived influence, is critical. In order to ensure the integrity of this research, any conflict of interest of persons who have a role in the design, conduct, analysis, publication or any aspect related to the trial will be disclosed and managed. The PI reports that this study is a work for hire by the Sponsor. There is no other known conflict of interest.

10.2 Additional Considerations

No additional considerations.

10.3 Abbreviations and Special Terms

Below is a list of abbreviation or special terms used in this study protocol.

AE	Adverse Event	
ANCOVA Analysis of Covariance		
CFR	Code of Federal Regulations	
CRF	Case Report Form	

eCRF	Electronic Case Report Forms		
FDA	Food and Drug Administration		
GCP	Good Clinical Practice		
HIPAA	Health Insurance Portability and Accountability Act		
ICH	International Council on Harmonisation		
IDE Investigational Device Exemption			
IRB	Institutional Review Board		
ITT	Intention-To-Treat		
LSMEANS	Least-squares Means		
NIH	National Institutes of Health		
NIH IC	NIH Institute or Center		
OHRP	Office for Human Research Protections		
PI	Principal Investigator		
QA	Quality Assurance		
QC	Quality Control		
SAE	Serious Adverse Event		
SAP	Statistical Analysis Plan		
SOP Standard Operating Procedure			
UP	Unanticipated Problem		
US	United States		

10.4 Protocol Amendment History

The table below is intended to capture changes of IRB-approved versions of the protocol, including a description of the change and rationale. A **Summary of Changes** table for the current amendment is located in the **Protocol Title Page**.

Version	Date	Description of Change	Brief Rationale

Appendix A: Online Survey Tool and Consent Form (Google Form)

This section shows what the Google Form will look like to the study participant. These are the questions the participant will be asked.

The first page of the study contains the consent form and the question that confirms the participant's agreement to participate.

There is skip logic for certain sections. For example, if the participant selects one cycle of using Mosie, the information related to cycles 2-6 will be skipped. If the participant selects that she is pregnant the questions related to the pregnancy will be asked, otherwise they will be skipped. If a donor was used, the questions related to producing a sperm sample will be skipped.

Note: Final language and questions might be tweaked or revised at any time to increase clarity.

MOSIE-001 © 2020 Mosie Baby Page 38

[figure not shown]
This is the inclusion/exclusion form.

If Participant selected to not participate in the study, he/she will see this screen next. If the participant said he/she is not 18 or older or has not used Mosie this screen will be displayed.

[figure not shown]

Qualifying participants will continue the survey on this page.

[figure not shown]

[figure not shown]
	ch of these diagnoses or issues do you believe are contributing to your rtility? *
	Not applicable
	PCOS
	Endometriosis
	Low AMH or low ovarian reserve
	Low Sperm count
	Sperm motility issues
	Erectile Dysfunction
	Performance issues or sexual anxiety, or inability to orgasm with partner
	Vaginismus or vulvodynia
	Tilted Uterus
	Multiple uterus/cervix
	Unexplained infertility
	Have only one functioning fallopian tube
П	Other:

[figure not shown]
No other method	is attempted			
Male/Female into	ercourse			
IVI or syringe oth	ner than Mosie			
IUI				
Femara				
Clomid				
IVF				
Cervical Cap				
Other:				
	None	1	2	3 or more
How many pregnancies have you had?	0	0	0	0
pregnancies	0	0	0	0
pregnancies have you had? How many live births have you had? How many pregnancies have you had that were	0	0	0	0
pregnancies have you had? How many live births have you had? How many pregnancies have you had	0	0	0	0

[figure not shown]

[figure not shown]
	0	1	2	3+
24-48 hours prior to ovulation	0	0	0	0
within 24 hours of ovulation	0	0	0	0
24-48 hours after ovulation	0	0	0	0
48+ hours after ovulation	0	0	0	0
Did you use Mosie fo Yes No	or another cy	cle?		

[figure not shown]

[figure not shown]

[figure not shown]

[figure not shown]

Mosie Kit Survey

* Required

[figure not shown]
How did you or your partner time your ovulation? (Select all that apply.) *
Count days in cycle
Track vaginal or cervical fluids
Tracking changes in the cervix
Use ovulation predictor kit
Use an app to estimate ovulation
Basal Body Temperature
Wearable device
Did not time ovulation
Did using Mosie result in a pregnancy? *
O Yes
O No
Back Next Page 10 of 20

[figure not shown]
Never submit passwords through Google Forms.

 $This \ content \ is \ neither \ created \ nor \ endorsed \ by \ Google. \ \underline{Report \ Abuse} - \underline{Terms \ of \ Service} - \underline{Privacy \ Policy}$

Google Forms

Page 56

[figure not shown]

Safe process

Enjoyable

	Very Easy	Easy	Neutral	Difficult	Very Difficult
To collect the semen/sperm sample in the cup?	0	0	0	0	0
To draw up the semen/sperm in the syringe?	0	0	0	0	0
Insert the Mosie syringe into the vagina up to the handles?	0	0	0	0	0
To deposit the semen/sperm at or near the cervix using the syringe?	0	0	0	0	0
My overall impression on the ease of use	0	0	0	0	0
					Page 12 of 20
submit passwords to	through Google Fo				

MOSIE-001 © 2020 Mosie Baby Page 59

MOSIE-001 © 2020 Mosie Baby

Page 60

Pulled the syringe plunger back and forth to confirm it was functioning.

My partner washed their hands

Use a sperm friendly-lubricant.

Thawed out donor sperm from sperm bank

Prepared all items and have them handy ready to use.

Washed the penis

that	apply)?*
	Lie down in a comfortable position.
	Relax
	Receive oral sex
	Stimulate clitoris
	Use any vibratory or non-vibratory stimulation device intravaginally
	Have an orgasm
	Other:
	erall, how well were you able to use the Mosie syringe to inseminate yourself our partner? * Very Able
	our partner? *
or y O O O	our partner? * Very Able Able Not Very Able
or y 0 0 0 0	Very Able Able Not Very Able Not Able at All Volume at All Volume at All Volume at All Volume at All Able at All Volume at All Able at All Able at All
or y O O O	Very Able Able Not Very Able Not Able at All Volong did you remain laying down after using the Mosie syringe? * Less than 15 minutes

Willelf best descri	ibes your lying position? *	
On my stomach	n	
On my side		
On my back		
On my back wit	th my hips elevated by a pillow	
Other:		
O No		
O		
What type of sam	ple did you use? *	
What type of sam	ople did you use? * rom a sperm bank (frozen)	
What type of sam	rom a sperm bank (frozen)	

0 2000	thank 50%	
O 51%-	70%	
O 71% -	80%	
O 81%-	90%	
O 90%-	95%	
O 96%-	100%	

Mosie Kit Survey

* Required

Sperm Collection Process

[figure not shown]
How easy was it for you or your partner or known donor to deposit the sample into the cup? *

- O Very Difficult
- O Difficult
- O Easy
- O Very Easy

How stressful was the experience for your partner or donor to produce a semen sample at home (view point of the person providing the sperm)? *

[figure not shown]
- Not Stressful at all
- A Little Stressful
- Moderately Stressful
- O Very Stressful
- O Extremely Stressful

пач	e you or your partner had to produce a semen sample at a doctors office? *
0	Yes
0	No
To	what degree do you agree or disagree with the following statement:
Pro	ducing a sample at home was a lot less stressful than at the doctor's office.
0	Strongly Agree
0	Agree
0	Neutral
0	Disagree
0	Strongly DIsagree
Bac	k Next Page 14 o
Dac	k Next Page 14 o
er su	bmit passwords through Google Forms.
-	This content is neither created nor endorsed by Google. Report Abuse - Terms of Service - Privacy Policy

[figure not shown]
*	v would you rate your level of concern over the safety of using the Mosie Kit?
0	Not concerned at all
0	A little concerned
0	Somewhat concerned
0	Very concerned
0	Extremely concerned
	to help resolve the infection? (Please answer this on behalf of the personing Mosie to conceive.) *
usir	Account of the experience of the control of the con
O	Not Applicable: Did not have any vaginal infections
0	Nothing, it resolved on its own
_	
0	Douche or wash
0	Douche or wash Used over the counter (OTC) medications

olicable				
a or Yeast Infecti	on			
ginitis				
niniasis				
Next)	■ Page 15 of 20
words through Goo	gle Forms.			
	ginitis niniasis	ginitis	ginitis niniasis	ginitis niniasis Next

[figure not shown]

	I did not talk to my doctor
\circ	Strongly agree
\sim	
0	Agree
O	Neutral
0	Disagree
0	Strongly disagree
0000	I did not talk to my doctor Strongly agree Agree Neutral
0	Disagree
0	Strongly disagree
	our doctor had any concerns over using Mosie, would you please share them

	I would recommend Mosie to other people in my same situation. *
	O Strongly agree
	O Agree
	O Neutral
	O Disagree
	O Strongly disagree
	Overall how many stars would you give Mosie? Choose
	Back Next Page 16 of 20
Neve	er submit passwords through Google Forms.
	This content is neither created nor endorsed by Google. Report Abuse - Terms of Service - Privacy Policy
	Google Forms

[figure not shown]
Page 17 of 2

What is your ra	ce/ethnicity? *	
Multiracial o	r Multiethnic	
Black or Afri	can American	
Hispanic or	_atinx	
· White		
Native Amer	ican or Alaska Native	
Native Hawa	iian or other Pacific Islander	
Asian Ameri	can	
Indian Amer	can	
Other		
What is your ap	proximate household income?*	
Choose	•	

Hov	v would you describe yourself? *
0	Woman
0	Man
0	Transgender
0	Non-binary
0	Prefer not to say
0	Other:
0	Single/Not in a relationship LGBTQ Relationship Other:
Are	you married? *
0	Yes

	ID 17 directed you	ır family building	plans? *	
O Yes				
O No				
If yes, pl	ease share how it h	as affected you	r family building	g plans.
Your ansv	ver			
Is there	anything else you w	ould like to sha	re with us?	
Your answ	ver			
	Next			Page 1
Back				, and the second
	asswords through Googl			

Mosie Kit Survey

THANK YOU! We so appreciate you!

Use code WARMHUGS for 15% off your next purchase.

If you did conceive with the Mosie Kit, we'd love to celebrate your joyful news and send you a special baby gift. Email us at [contact] to share your news!

If you're still on your journey to conceive, we are sending you big hugs! We want to help and support you as best we can, no matter the path taken, we are here for you! If you have any questions or if you're interested in sharing your current journey to conceive with the Mosie Community, email us at [contact]. Fingers crossed for you!

Our thanks and best wishes to you! Team Mosie Baby

This content is neither created nor endorsed by Google. Report Abuse - Terms of Service - Privacy Policy

Google Forms

MOSIE-001 © 2020 Mosie Baby Page 79

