Analysis: Descriptive statistics surrounding the ease of use on a 5-point likert (very easy to very difficult) will be analyzed on five different aspects of use. Specifically, the steps of using the Mosie Kit (collecting a sperm sample, drawing up the sample in the Mosie syringe, inserting the syringe, and depositing the sperm at or near the cervix) and overall ease of use will be examined. Additionally questions related to use such as comfort, ease and safety of the process, enjoyable and intuitiveness of use (able to use it without instructions) will allow the user to rate their experience from Strongly agree to strongly disagree (5 point scale). The data will be plotted and examined as part of the analysis.

Secondary Hypothesis 2: The participants were able to use the Mosie Kit as instructed using the instructions contained in the kit. The alternative hypothesis is that the participants were not able to use the kit using the instructions contained in the kit.

Analysis: Descriptive analysis of perceived overall success rate will be analyzed. Additionally, descriptive analysis of the frequency of each expected behavior related to use of the kit will be examined.

Secondary Hypothesis 3: The participants reported they used the kit as intended, specifically, using it within 24 hours of initial signs of ovulation and again 24-48 hours after ovulation was confirmed or expected. The alternative hypothesis is that the participants report they did not use the kit as intended with respect to timing (within 24 hours of initial signs of ovulation and again 24-48 hours post ovulation).

Analysis: Frequency rates related to timing of insemination at all reported cycles will be analyzed. The data will be reported in both total number of attempts at each time point as well as percentage of attempts at each time point in comparison with total cycles where the Mosie Kit was used. T-tests will also be used in this analysis. Additionally,

amount of time lying after insemination and position of lying will be analysed using descriptive statistics and correlations with pregnancy rate.

Secondary Hypothesis 4: Participants reported they perceived the Mosie Kit to be a safe way to conceive. The alternative hypothesis is that participants did not perceive the Mosie Kit to be a safe way to conceive.

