9.2 Sample Size Determination

The desired final sample size for this study is 500 completed surveys. This will produce a 95% confidence interval with +/- 4.4% within larger populations. In order to obtain that rate of respondents, the study will invite about 50% people who have ordered a Mosie Kit in the prior 2-8 months to the study start date. It is expected that approximately 4000 people will be invited to participate. By inviting 4000 potential participants, it is expected that with a response rate of 15% approximately 600 will complete the survey. Currently Mosie has about a 20% open rate on their general emails. For this reason, all people who purchased a kit within the last 2-8 months will be invited to participate.

According to the sample size tables, a response rate of 384 is sufficient to provide a 95% confidence interval with a 5% margin of error rate. While the total number of respondents can not be controlled, every effort will be made via the reminder emails to obtain at least 500 participants but no less than 384.

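### Appendix A's skip rule sends all donor users past the sperm-collection page, yet that page's questions name known donors, so the two must be reconciled

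*Combined protocol and SAP*

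**What the plan says.** The introduction to Appendix A describes the survey's branching by example. On donors it says: "If a donor was used, the questions related to producing a sperm sample will be skipped". No type of donor is specified.

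The Sperm Collection Process page (survey page 14 of 20) has two items on collecting the sample at home:

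- Ease of deposit: "How easy was it for you or your partner or known donor to deposit the sample into the cup", with four options from very difficult to very easy.
- Stress at home: "How stressful was the experience for your partner or donor to produce a semen sample at home", with five options, to be answered from the viewpoint of the person who provided the sperm.

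Two other survey items matter here. An ease-of-use grid on survey page 12 includes the row "To collect the semen/sperm sample in the cup" on a five-point scale. A sample-type question, which begins "What type of sam" and is cut off in the extracted text, comes after that grid and before page 14. Its one fully legible answer is a frozen sperm-bank sample.

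On analysis, Section 9.4.1 promises descriptive statistics for every survey question. Section 9.1 lists what Secondary Hypothesis 1 will examine: "Specifically, the steps of using the Mosie Kit (collecting a sperm sample, drawing up the sample in the Mosie syringe, inserting the syringe", then depositing the sperm, plus overall ease, all on a five-point scale.

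**The concern.** The rule and the page disagree about who should answer. The rule excludes anyone who used a donor, while the page asks for the experience of known donors. A known donor who produces a fresh sample at home performs the very step that the page asks about. A frozen bank sample involves no collection at home.

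If the rule is programmed as written, the page-14 results cover partner samples only, while the published question wording tells a reader that donors are included. Section 4.3 says that no follow-up is possible, so the missing answers could not be obtained afterwards. What is at stake is who contributes to two descriptive results, and whether those results are labelled correctly.

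**Working it through.** The point rests on comparing texts. The plan states no figure for it to reproduce.

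**Step 1. Who sees the page, and whom it addresses**

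| Source of sample | Collected at home? | Skip rule as written | Page-14 wording |
|---|---|---|---|
| Respondent or partner | Yes | Shown | Named |
| Known donor, fresh sample | Yes | Skipped | Named in the ease item; covered by donor in the stress item |
| Frozen sperm-bank sample | No | Skipped | Not applicable |

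The conflict is confined to the second row. Skipping bank users is sensible, because both items are marked as required and no not-applicable option is visible.

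**Step 2. Which planned analysis uses the page**

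The Secondary Hypothesis 1 analysis in Section 9.1 has four steps plus overall ease, on five points from very easy to very difficult. The page-12 grid has the same four steps, an overall row and the same five points. The page-14 ease item has four points and no neutral option, so it is not the measure that Section 9.1 describes. None of the hypotheses in Section 9.1 names the page-14 ease or stress items. They fall under the per-question descriptives of Section 9.4.1.

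**Step 3. Can the effect be sized?**

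Let *d* be the known-donor share of those who collected at home, *a* the proportion of partner users giving some answer, and *b* the proportion of known-donor users giving it. Then

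reported minus intended = *a* − [(1 − *d*)*a* + *d* *b*] = *d*(*a* − *b*).

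The documents give none of *d*, *a* or *b*. As a pure assumption, take *d* from 10% to 50% and a gap between the groups of 10 to 25 points in either direction:

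- smallest: 0.10 × 0.10 = 0.01, or 1 point;
- largest: 0.50 × 0.25 = 0.125, or 12.5 points.

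The sign follows whichever group reports the higher rate. With no gap, the shift is zero. This is no estimate; it shows that the documents fix neither size nor direction.

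**Step 4. Precision**

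Section 9.2 says: "The desired final sample size for this study is 500 completed surveys", with a half-width of 4.4%. Check: 1.96 × √(0.25/500) = 4.38%, which agrees.

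The known-donor share is again an assumption. If 5% to 30% of the 500 used a known donor, 25 to 150 people are routed past the page. Ignoring the bank users who rightly skip it:

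- 475 answer: 1.96 × √(0.25/475) = 4.5%;
- 350 answer: 1.96 × √(0.25/350) = 5.2%.

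Over that range the loss of precision is small. The real loss is that a group named in the questions is absent.

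**The case against.** The strongest reply is that the rule is a one-line summary, introduced as an example, of a form shown mainly as screenshots. Those images and most of the sample-type answers are not legible in the text, so the real branching cannot be inspected. Donor may be shorthand for a bank donor; a preparation item elsewhere in the survey does link donor sperm with a sperm bank. On that reading the form already works.

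This stands as a limit on what can be claimed: a faulty form is not proved. It does not remove the conflict. The survey separates known donors from bank sperm elsewhere, the rule does not, and nothing in Appendix A says which is meant. The note that wording may be revised for clarity does not settle it either.

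Three stronger readings are tempting, and the objection to each is sound.

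- *Secondary Hypothesis 1 is compromised.* A reader might infer this because collecting the sample is one of its steps. The matching item is in the page-12 grid, ahead of the only legible sample-source question, and nothing shows that known-donor users miss it. That would change only if the rule, which is worded by question content, were also applied to the grid.
- *The results are biased by a known amount or in a known direction.* No donor share or response rate is given. A result for partner users only, labelled as such, is a matter of scope.
- *Most LGBTQ and single users who collected at home are lost.* Some of them may depend on a known donor, but the documents give no breakdown of sample source by relationship type.

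**Conclusion.** The point holds in a narrow form. The stated rule contradicts the instrument. If it is implemented literally, the two page-14 results, ease of deposit and stress at home, leave out the known-donor users whom the questions address, and this cannot be repaired after data collection.

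The conclusion assumes that the form follows the rule as written and that some respondents used a known donor who collected at home. The documents confirm neither. The size and direction of any effect on the reported percentages are unknown. The primary endpoint is untouched, and no effect on a named hypothesis has been shown. This is a minor correction, worth making because it is nearly free.

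**What to change.** Reconcile the Appendix A skip rule with the Sperm Collection Process page before the form opens. State the rule by whether a sample was collected at home: skip the page only when none was, for example with a frozen sperm-bank sample, and show it to partner and known-donor users. The sample-type question comes before page 14 and could drive the branch. The sponsor should check its full list of answers for any other option without a home collection step, since those answers are not legible here.

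The cost is one branching condition, one amended sentence in Appendix A, and a few extra questions for known-donor users. If the form already branches this way, only the sentence needs to change.
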